8. ENDPOINTS AND COVARIATES

The following endpoints will be estimated.

Primary objective: To describe the baseline demographic, clinical (including previous treatment) and laboratory characteristics of patients with relapsed/refractory B-cell ALL at initiation of treatment with InO.

Summary measures of:

- *Demographic characteristics:*
 - *Age at index date;*
 - *Sex.*
- *Clinical characteristics:*
 - *ECOG performance status at baseline;*
 - *Time between ALL diagnosis and index date;*
 - *Phase of disease at index date: CR, 1st relapse, 2nd relapse, 3rd relapse, 4th or greater relapse;*
 - *CD22 expression: percentage of positive cell blasts;*
 - *ALL cytogenetics; mixed lineage leukaemia (MLL)-AF4; BCRABL; low hypodiploidy/near triploidy; complex karyotype;*
 - *Number of ALL relapses prior to index date;*
 - *History of liver diseases prior to index date (before or after diagnosis), and whether they were ongoing or resolved at index date.*
- *Laboratory characteristics at baseline:*
 - *Full blood counts, including platelets and ANC;*

- *Liver function tests including alanine aminotransferase (ALT), aspartate aminotransferase (AST), alkaline phosphatase (ALP), bilirubin, albumin, gamma glutamyl transferase (GGT).*
- *ALL-related treatment prior to InO initiation:*
 - *1st line chemotherapy according to national trial or treatment guideline;*
 - *Summary of number of patients by;*
 - *Number of lines of salvage therapy: 0, 1, 2, ≥ 3 ;*
 - *Number of prior HSCT (0, 1, 2, ≥ 3);*
 - *Type of conditioning regimen for each HSCT (high dose myeloablative, reduced intensity, nonmyeloablative);*
 - *Treated with blinatumomab;*
 - *Number of CAR T-cell therapies: 0, 1, ≥ 2 .*

Secondary objective 1: To describe the InO treatment pathway, including InO doses, dose modifications and number of cycles of treatment; and concomitant medications.

- *Total duration of treatment with InO;*
- *Number of cycles of InO per patient;*
- *Interrupted cycles of InO, including reasons (liver toxicity TRAEs, other AEs, tolerance, treatment failure, and course complete);*
- *Doses of InO prescribed;*
- *Modification of doses of InO, including reasons (liver toxicity TRAEs, other AEs, tolerance, treatment failure, and course complete);*
- *Azole antifungal therapy concomitant to InO treatment.*

Secondary objective 2: To summarise CR/CRi rates following initiation of InO, overall and according to the number of salvage therapies received prior to InO initiation.

Summary measures of:

- *CR, CRi and CR/CRi response rates by the end of InO treatment, overall and according to the number of salvage therapies in the pre-index observation period (0, 1, ≥ 2).*

- *Median time to CR/CRi (95% CI).*

Secondary objective 3: To summarise MRD negativity rates following initiation of InO and describe the number of cycles of InO needed to attain MRD negativity.

- *Number and proportion of patients achieving a MRD negative CR/CRi overall and by the number of completed cycles of InO (after 1, 2, ≥ 3 cycles of InO) in patients evaluated by flow-cytometry/ molecular assessment / both.*

Secondary objective 4: To describe OS, and cause of death; in all patients and in patient with or without follow-up HSCT.

- *The number and proportion of patients surviving at 3, 6 and 12 months after InO initiation;*
- *Cause of death;*
- *Median OS (95% CI).*

Secondary objective 5: To describe RFS in all patients and in patients with or without follow-up HSCT. Additionally, to describe NRM in patients undergoing follow-up HSCT.

- *The number and proportion of patients who are relapse-free at 3, 6 and 12 months after InO initiation;*
- *Median RFS (95% CI).*

In patients undergoing follow-up HSCT:

- *Median NRM (95% CI) from the date of follow-up HSCT.*

Secondary objective 6: To describe the treatments for ALL and responses to treatment post-InO, including HSCT, chemotherapy regimens and CAR T-cell therapy

For each treatment post-InO including new chemotherapy (blinatumomab, CarT, other), HSCT, CAR T cell therapy, report:

- *Number and proportion of patients initiated on treatment (for HSCT report number of HSCT);*
- *Response to treatment: CR, CRi, progressive disease, stable disease;*
- *Survival: number of patients alive / dead at completion of treatment.*

Secondary objective 7: To describe the occurrence of safety events including documented diagnosis of VOD/SOS, grade 3/4 TRAEs (lung/cardiac/kidney) and other liver dysfunction following InO initiation; in all patients and in patients with or without follow-up HSCT. In addition, to evaluate associations between risk factors identified in the INO-VATE ALL trial and risk for VOD/SOS in patients with follow-up HSCT.

Summary measures of, in all patients, and separately in patients with and without follow-up HSCT:

- Number and proportion of patients experiencing a documented diagnosis of VOD/SOS during the post-index observation period, overall, by grade, and in the subsets of patients (1) with follow-up chemotherapy after completion of chemotherapy, and (2) with follow-up HSCT after HSCT Separate;
- Treatments received for documented diagnoses of VOD/SOS including defibrotide and heparin and survival following treatment (patient alive / dead, cause of death);
- Number and proportion of patients with InO discontinuation due to VOD/SOS;
- Number and proportion of patients experiencing grade 3/4 TRAEs (following InO initiation, by type);
- Treatments received and InO dose delay/reduction/discontinuation for grade 3/4 TRAEs (lung/cardiac/kidney);
- Number and proportion of patients experiencing other liver dysfunction following InO initiation);
- Treatments received and InO dose delay/reduction/discontinuation for other liver dysfunction;
- Peripheral blood blast counts of patients prior to follow-up HSCT;
- Number and proportion of patients with significant risk factors for VOD/SOS measured at the time of follow-up HSCT, separately in patients developing and not developing VOD/SOS.

Secondary objective 8: To describe overall HSCT rate and rate in patients going directly into HSCT (eg, without another induction therapy)

Exploratory endpoint:

- CCI [REDACTED]

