
 • Cycle number • PCR results providing percentage of leukaemic cells in bone marrow nucleated cells • Or alternatively, immunophenotyping by flow-cytometry results providing percentage of leukaemic cells in bone marrow nucleated cells 					
ALL diagnosis: • Date of first diagnosis.	✓	✓			

INOTUZUMAB
X9001222 NON-INTERVENTIONAL STUDY PROTOCOL
V1.0, 18 July 2019

Variables	Study time points				
	Pre-index observation period	Baseline	Index date	Post-initiation observation period	Other

 Phase of disease at receipt of Inotuzumab CR, 1st relapse, 2nd relapse, 3rd relapse, 4th or greater relapse CD22-expression test results: positive/negative Cytogenetic test result: MLL- AF4; BCR-ABL; low hypodiploid/near triploidy; complex karyotype e Relapsed at index date: Yes/No Refractory at index date: Yes/No 					
Liver diseases diagnosed prior to index date: 
 Name date diagnosis Diagnosed before/after ALL diagnosis at index date, ongoing / resolved 	✓	✓			
Full blood counts, date, result (including unit) for: 
 platelets ANC 		✓	✓		
Liver function tests: date, result and ULN for: 
 ALT AST ALP Bilirubin Albumin gamma glutamyl transferase. 		✓	✓	✓ for ALT, AST and bilirubin in patients with follow-up HSCT, at time of follow-up HSCT (up to 3 months before)	
Peripheral blood blast counts of patients				✓ in patients with	

PFIZER CONFIDENTIAL

INOTUZUMAB
X9001222 NON-INTERVENTIONAL STUDY PROTOCOL
V1.0, 18 July 2019

Variables	Study time points				
	Pre-index observation period	Baseline	Index date	Post-initiation observation period	Other
				follow-up HSCT, at time of follow-up HSCT (up to 3 months before)	
ALL relapses prior to InO: 
 • date of relapses • Name, start and stop dates, and best response to treatment for relapses prior to InO (list to be determined and may include: fludarabine- and anthracycline-containing regimens, blinatumomab) 					
Treatment history for ALL (all since diagnosis) prior to InO: 
 • 1st line chemotherapy according to national trial or treatment guideline • Blinatumomab treatment • Number of lines of salvage therapy • Prior HSCTs: number (0, 1, 2, ≥ 3) and type of conditioning regimen for each HSCT: high-dose myeloablative, reduced-intensity, nonmyeloablative • CAR T-cell therapies: number (0, 1, ≥ 2) 	✓	✓			

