ALL refractory prior to InO: 
 • Name, start and stop dates, and best response to treatment prior to InO 	✓	✓			
Concomitant medication to InO		✓ (if	✓	✓	

PFIZER CONFIDENTIAL

Variables	Study time points				
	Pre-index observation period	Baseline	Index date	Post-initiation observation period	Other
treatment: • Azole antifungal therapy including fluconazole, voriconazole, itraconazole and posaconazole: date started, date end		medication during InO treatment)			
AEs: name, date start, date end, grade, treatment given and response to treatment: • Documented diagnoses of VOD/SOS • grade 3/4 TRAEs affecting the lung, cardiac system, or kidney		✓		✓	
For each HSCT after initiation of InO: • date • InO treatment completed at HSCT: Yes / No • Conditioning regimens prior to HSCT including Busulfan other alkylating agents (names and date start, date end); full intensity / reduced intensity conditioning • Response to HSCT: CR, CRI, progressive disease, stable disease, alive/dead after HSCT				✓	
Chemotherapy treatment after initiation of InO: • name, regimen, start date • Response to chemotherapy treatment: CR, CRI, progressive disease, stable disease, alive/dead at end of treatment				✓	
CAR-T cell therapy after InO: • start date • response to CAR-T cell therapy: CR, CRI, progressive disease, stable disease, alive/dead at end of treatment				✓	
Patient status at the end of data collection period (alive/dead) • date of death / last clinic visit • Cause of death • If not known (i.e. lost to follow-up),				✓	

Variables	Study time points				
	Pre-index observation period	Baseline	Index date	Post-initiation observation period	Other
date of last recorded hospital visit.					

Note: All dates are DD/MM/YYYY for all patients, except for date of birth (MM/YY). If dates are not available as DD/MM/YYYY, dates will be recorded as MM/YYYY instead.

List 1. Operational definitions for clinical endpoints

Salvage therapy: therapy initiated in patients in whom initial induction therapy does not achieve remission (refractory ALL) or patients who entered remission and then subsequently relapsed (relapsed ALL), with the aim to induce remission of ALL.

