3.1.1. Key Definitions

- *Index date: the date of initiation of the first cycle of InO.*

[figure not shown]
- *Baseline period: period from 6 months prior to index date. The closest observation recorded during the baseline period to the index date will be used as baseline data (when more than one observation is available).*
- *Pre-index observation period: period from the date of ALL diagnosis to the index date.*
- *Post-index observation period: period from the index date until the date of death, or date of latest visit at the time of data collection, whichever is soonest.*
- *CR/CRi rate: number of patients who achieve CR/CRi divided by the total number of patients completing treatment with InO (defined as patients with a recorded date of discontinuation of InO).*
- *MRD negativity rate: proportion of patients in whom MRD-negative status is observed, among patients in whom MRD negativity status has been assessed, at any time until the end of treatment with InO (defined as the date of recorded discontinuation of InO).*
- *OS: time from index date to death.*
- *RFS (interchangeable with EFS for the purpose of this SAP): time from index date to the earliest date of the following events: death, progressive disease (including objective progression, relapse from CR/CRi, treatment discontinuation due to global deterioration of health status) and start of new induction therapy or posttherapy HSCT without achieving CR/CRi.*
- *NRM: Time from the date of follow-up HSCT until death without disease progression or relapse. Deaths from any cause without prior progression are events. Events related to the disease such as relapse, progression are competing events, loss of follow-up are censored.*

Patients will be observed from the start of the pre-index observation period until the end of the post-index observation period. For the purpose of identifying risk factors for VOD/SOS and replicating the findings by Kantarjian et al¹ follow-up will be defined as the post-index observation period, and patients will be censored at the date of the last recorded clinic visit prior to data collection.

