3.1.2. Study Population

The source population for this study is adult patients treated with InO at the selected sites and who accessed InO via NHS commissioning, via the CUP or via private purchase between June 2016 and date of data collection (December 31st 2020). The NICE recommendation is as an option for treating relapsed or refractory CD22-positive B-cell precursor acute lymphoblastic leukaemia in adults; and patients with relapsed or refractory Philadelphia chromosome positive disease should have had at least 1 tyrosine kinase inhibitor. The eligibility criteria for inclusion into the CUP is provided in Section 16 Annex 1 of the study protocol.

Patients will be eligible for inclusion in the present study if they fulfil all the following criteria:

Inclusion Criteria

- *Patients with relapsed/refractory ALL.*
- *Patients who initiated InO between 1st of June 2016 and date of data collection (to be confirmed).*

- *Patients who accessed InO treatment via NHS commissioning, via the CUP, or via private purchase.*
- *Patients aged ≥ 18 years old at initiation of InO treatment.*

Exclusion Criteria

- *Patients initiated on treatment with InO at a different hospital than the ones selected in this study.*
- *Patients with < 3 months of follow-up since index date, unless death occurs < 3 months from index date.*

Consent will not be required as all identifiable patient data (from surviving and deceased patients) will be extracted by the patient's direct medical care team. Eligible patients will be selected by chronological order and with a priority given to patients treated via NHS commissioning, where possible.

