9. HANDLING OF MISSING VALUES

Where dates are ambiguous because of missing day and/or months, standard imputation will be applied: where day is missing the 15th of the month will be assumed; where both day and month are missing the 1st July will be assumed if appropriate to the analysis being conducted. The imputed dates for pre-index records will be reviewed to confirm they are prior to the index date, and the imputed dates for post-index records will be reviewed to confirm they are after the index date. Where data other than dates are missing from the original medical record, the affected analyses will be conducted using only the results of those patients with data available and the number included in each analysis will be stated. The percentage of data missing will be reported for each study variable. Note that the multivariate model will only include those patients with non-missing values for all covariates.

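### The disease-phase list has no level for primary-refractory patients, and it allows CR at index without a rule for counting those patients in the CR/CRi rate or time to CR/CRi

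*SAP*

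**What the plan says.** **Population.** SAP 3.1.2 admits "Patients with relapsed/refractory ALL", and the primary objective in SAP 8 describes "patients with relapsed/refractory B-cell ALL at initiation of treatment with InO".

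**Phase list.** SAP 8 gives the levels as "Phase of disease at index date: CR, 1st relapse, 2nd relapse, 3rd relapse, 4th or greater relapse". The same list appears in Protocol 9.3 (Table 1) and in Annex 2 (Table 4).

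**Refractory disease.** Annex 2 describes salvage therapy as "therapy initiated in patients in whom initial induction therapy does not achieve remission (refractory ALL"), so refractory there means that induction failed. Annex 2 collects "Refractory at index date: Yes/No", a matching item for relapsed status, and the treatment history under "ALL refractory prior to InO". SAP 8, 10.2.1 and 10.2.11 list no output for the two Yes/No items.

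**Missing values.** The phase row in SAP 10.2.11 gives exclusion as its missing-data rule. SAP 9 says that "the affected analyses will be conducted using only the results of those patients with data available". SAP 10.1.2 requires missing counts for categorical variables.

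**Response.** SAP 3.1.1 defines the CR/CRi rate as "number of patients who achieve CR/CRi divided by the total number of patients completing treatment with InO", where completing means having a recorded InO stop date. SAP 10.2.3 repeats this. SAP 10.2.11 measures time to best response from the start of InO. None of these sections sets a condition on remission status at index.

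**The concern.** The primary objective is purely descriptive, so its tables need a place for every eligible patient. A primary-refractory patient has never been in remission and so cannot have relapsed. If the patient is left out of the phase table, a known status is shown as missing and the percentages for the other levels rise. If the patient is put under a relapse level, the table is wrong.

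The CR level raises a separate question. CR and CRi are defined in Annex 2 as states (marrow blasts, peripheral blasts, counts, extramedullary disease), not as changes from baseline. A patient who enters in CR and stays there satisfies the definition at the first assessment, although he or she was never at risk of achieving remission on InO. That patient adds to both numerator and denominator of the rate and supplies an event to the Kaplan-Meier analysis of time to CR/CRi.

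**Working it through.** The documents state no figure that depends on this point, so there is nothing to reproduce. The check sets the definitions side by side and then illustrates the size.

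**Step 1: can every eligible patient be placed?**

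- Patient in first or later relapse: has a level.
- Patient refractory to salvage after a relapse: still has a relapse level.
- Patient in CR at index: has a level.
- Primary-refractory patient: has no level.

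The number-of-relapses row in SAP 8 helps only indirectly. Zero relapses fits a primary-refractory patient, but also one who failed induction, reached remission on salvage and started InO in CR.

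**Step 2: effect on the phase table.** Assume 25 patients (the target in SAP 3.1.3), 12 of them in first relapse, and *r* primary-refractory patients treated as missing. The first-relapse percentage is 12/(25 − *r*):

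- *r* = 0: 12/25 = 48%
- *r* = 1: 12/24 = 50%
- *r* = 3: 12/22 = 55%
- *r* = 5: 12/20 = 60%

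**Step 3: effect on the CR/CRi rate.** Let *N* = 25, *k* = patients in CR at index, *p* = response rate in the others, and *m* = share of the *k* patients still recorded in CR/CRi at end of InO. For simplicity all 25 have a recorded stop date.

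Rate with everyone counted = [*p*(*N* − *k*) + *mk*]/*N*

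Rise over *p* = (*k*/*N*)(*m* − *p*)

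The documents give no *k* or *m*, and no *p* for this cohort. The values are assumptions; the top value of *p* is the 80.7% CR rate that Protocol section 7 quotes from the phase III trial. With *m* = 1, the rise in percentage points is:

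| *k* | *p* = 50% | *p* = 65% | *p* = 80.7% |
|---|---|---|---|
| 1 | 2.0 | 1.4 | 0.8 |
| 2 | 4.0 | 2.8 | 1.5 |
| 3 | 6.0 | 4.2 | 2.3 |
| 5 | 10.0 | 7.0 | 3.9 |

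For example, *k* = 5 and *p* = 65% gives 13/20 = 65% (Clopper-Pearson 95% CI 41% to 85%) without these patients and 18/25 = 72% (51% to 88%) with them.

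With *m* = 0.8, the rise for *k* = 1 to 5 is 1.2 to 6.0 points at *p* = 50%, 0.6 to 3.0 points at *p* = 65%, and about zero at *p* = 80.7%.

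**Step 4: salvage strata.** SAP 7.3 reports the rate by number of salvage therapies where n > 5. In an assumed stratum of 8 with 2 patients in CR at index, both still in CR/CRi, 4/6 = 67% becomes 6/8 = 75%.

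**The case against.** A reader might infer more than the documents support, in four ways.

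- **That refractory patients as a group drop out.** Only primary-refractory patients lack a level. Even for them, applying the exclusion rule to a known but unlisted status is an inference. It affects one row, and the missing count would be visible. The relapse-count row gives an indirect view, and Protocol 9.3 leaves response options to be detailed in the eCRF, which is not available here. What stands is that the printed lists have no such level and the SAP plans no direct report of refractory status.
- **That a patient in CR at index is a responder automatically.** Protocol 9.3 takes the first response recorded after end of treatment, with progression as an option, and Annex 2 defines the rate at end of treatment. A patient who progresses by then would not count. What stands is that a patient who simply remains in CR can count.
- **That such patients have response times close to zero.** Annex 2 dates response from records made by treatment cycle, after InO has started. Nothing assigns a baseline remission a time at or near index. What stands is that no rule says how they enter this analysis.
- **That the CR level contradicts the entry criterion.** The inclusion line does not expressly require active disease at index, so relapsed ALL in a later remission can be read as eligible. The access criteria that might settle this are stand-alone documents. The two passages are unreconciled rather than contradictory.

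It is also fair to say that the study tests no hypothesis and already warns of wide intervals (Protocol 9.9), and that any bias is likely to be small beside that imprecision. That limits the importance of the point without closing either gap.

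**Conclusion.** Both gaps are real. The phase list omits an eligible group that the protocol itself defines, in a primary-objective table, while the items that would identify the group are specified for collection and not reported. The plan also foresees patients in CR at index but lets them enter the CR/CRi rate and time to CR/CRi with no baseline condition, so a patient can count as a responder without any change in status.

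The size is unknown and probably modest: about 1 to 10 points on the overall rate under the assumptions above with everyone in CR at index remaining in CR/CRi, and less or nothing if some lose it. The numbers of primary-refractory and CR-at-index patients are assumptions, and either could be zero. The point merits correction because the remedy is cheap, not because it threatens the study.

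**What to change.** 1. Add a primary-refractory level to the phase list, and tabulate the two Annex 2 items (relapsed at index, refractory at index) in SAP 10.2.1 and 10.2.11.
2. Keep the CR level. Deleting it would leave those patients with no category and remove the listed baseline item that identifies them directly. State whether CR at index is compatible with eligibility.
3. If it is, compute the CR/CRi rate (overall and by salvage stratum) and time to CR/CRi in patients not in CR/CRi at index. Show the CR-at-index patients separately and keep them in the MRD, OS and safety outputs. SAP 10.2.4 restricts the MRD denominator to patients who achieved CR/CRi, so it should say explicitly that they remain in it.

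The cost is a slightly smaller CR/CRi denominator, a table row or two, and matching wording in SAP 8, the protocol lists (9.3 and Annex 2) and the eCRF. The fields are already specified in Annex 2. Because the list belongs to the primary objective, the sponsor should also decide whether the change falls under the amendment provision in Protocol 9.7.

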9. HANDLING OF MISSING VALUES

Where dates are ambiguous because of missing day and/or months, standard imputation will be applied: where day is missing the 15th of the month will be assumed; where both day and month are missing the 1st July will be assumed if appropriate to the analysis being conducted. The imputed dates for pre-index records will be reviewed to confirm they are prior to the index date, and the imputed dates for post-index records will be reviewed to confirm they are after the index date. Where data other than dates are missing from the original medical record, the affected analyses will be conducted using only the results of those patients with data available and the number included in each analysis will be stated. The percentage of data missing will be reported for each study variable. Note that the multivariate model will only include those patients with non-missing values for all covariates.

